APPENDI	X D. SOP INA-RESPOND, Specimen Ownership, Access, and Use
REFEREN	CES

GLOSSARY

02000/	
AE	Adverse Event
AFB	Acid-Fast Bacilli
ALT	Alanine Amino Transferase
AST	Aspartate Amino Transferase
BCG	Bacille-Calmette–Guérin
BMI	Body Mass Index
BW	Body Weight
CBC	Complete Blood Count
CRF	Case Report Form
DM	Diabetes Mellitus
DOTS	Directly Observed Treatment, Short course
DR-TB	Drug-Resistant Tuberculosis
DS-TB	Drug-Susceptible Tuberculosis
DST	Drug Susceptibility Testing
DNA	Deoxyribonucleic acid
EC	Ethics Committee
EOS	End of Study
ESR	Erythrocyte Sedimentation Rate
GCP	Good Clinical Practice
HIV	
ICH	Human Immunodeficiency Virus International Conference on Harmonization
ICF	Informed Consent Form
INA-RESPOND	Indonesia Research Partnership on Infectious
Disease IPR	Intellectual Property Rights
IRB	Institutional Review Board
MDR-TB	Multidrug-Resistant Tuberculosis
MGIT	Mycobacteria Growth Indicator Tube
MOP	Manual of Procedures
N	Number (typically refers to participants)
NIAID	National Institute of Allergy and Infectious Diseases
NIHRD	National Institute of Health Research and Development
NTP	National Tuberculosis Program
OHRP	Office for Human Research Protections
PBMC	Peripheral Blood Mononuclear Cell
PI	Principal Investigator
PMDT	Programmatic Management of Drug-Resistant TB
SAE	Serious Adverse Event
SoC	Standard of Care
ТВ	Tuberculosis
WHO	World Health Organization
XDR-TB	Extensively Drug Resistant Tuberculosis

Table of Figures

Table of Tables

Table 4.4. 1 Expected confidence bounds based on observed MDR proportions	amongst
previously treated TB cases	12
Table 4.4. 2 Expected confidence bounds based on observed MDR proportions amor	ngst new
TB cases	

RESEARCH SUMMARY

Title	INA102 - Tuberculosis Research Of INA-RESPOND on Drug
	Resistance (TRIPOD)
Study Type	Prospective Observational Study
Principal Investigator	Dr. dr. [name], M.Sc, SpP(K)
	dr. [name], SpMK,PhD
Sample Size	This study will analyze 500 participants bacteriologically
	confirmed TB (250 new cases and 250 previously treated
	cases). To obtain the numbers, we estimated that we need to
	enroll 1357 presumptive TB patients as participants (1000 new
	cases and 357 previously treated cases). These numbers were
	made based on our estimation that 25% of presumptive new TB
	cases and 70% of presumptive previously treated TB cases will
	be bacteriologically confirmed.
Study Population	Presumptive TB patients, \geq 18 years old
Study Duration	Up to 4.5 years
Accrual Period	Up to 2 years
Study Design	This study is a prospective observational cohort study of TB
	patients who are treated or evaluated at 10 study sites.
	Patients presenting with cough for 2 weeks or longer with at
	least one additional TB symptom and a chest X-ray suggestive
	of TB, will be invited to be enrolled in the study. The signed
	informed consent will designate their willingness to participate
	on this study. Enrolled participants will produce the sputum
	for bacteriological examination of M. tuberculosis by AFB,
	culture and Xpert. The sputum will also be tested by Xpert
	for drug resistance test. If the culture is positive, conventional
	DST will be performed, and M. tuberculosis isolates will be
	stored for spoligotyping and for future research on TB. All
	participants treated by TB drugs regimen will be followed for
	outcome assessment. For all enrolled participants, chest X-Ray
	results, demographic data, co-morbidities, symptoms, nutritional
	status, treatment regimens, compliance and outcome will be
	collected. In addition, sputum, blood, urine, and saliva will also
	be collected for related TB future testing.

Primary Objective	To estimate the proportion of MDR-TB amongst new and
	previously treated TB cases.
Secondary Objectives	
	j. Treatment regimens

1. BACKGROUND

Tuberculosis (TB) continues to be a major health problem in the world, especially in developing countries. Despite the use of anti-TB treatments and Bacille-Calmette-Guérin (BCG) vaccination, TB incidence continues to rise. It was declared a global health emergency by the World Health Organization (WHO) in 1995.¹ In 2015, WHO estimated that there were 10.4 million new TB patients with mortality rate of 1.8 million patients per year throughout the world.²

Based on the WHO Report 2016, Indonesia ranked second in the world with an estimated incidence in 2015 is 1,020,000 cases with mortality number 126,000.² This condition is exacerbated by the increasing incidence of diabetes mellitus (DM) and Human Immunodeficiency Virus (HIV) as TB comorbidities and the growing number of cases with Multidrug- Resistant TB (MDR-TB) or even Extensively Drug-Resistant TB (XDR-TB). This situation will lead to an epidemic of TB that is difficult to manage and continues to be a major public health problem.^{1,2,4} Previous TB drug resistant surveys conducted across Indonesia revealed that in Timika district, Papua (2004), 2% of new TB cases are MDR-TB cases, in Central Java province (2006), 1.8% of new TB cases and 17.1% of previously treated TB cases are MDR-TB. WHO Report 2016 estimation in 2015 for Indonesia gave a number of incidence which are 2.9% of new TB cases and 16% of previously treated TB cases are MDR-TB cases.^{2,5,7}

The Indonesia Health Profile study reported 194,000 new TB cases in 2011 based on positive smear results.⁸ TB control efforts were implemented in Indonesia starting in 1969 and Directly Observed Treatment Short-course (DOTS) began in 1995. Nevertheless, these efforts to date have not eliminated the TB burden.⁹ In 2009 Ministry of Health started the implementation of Programmatic Management of Drug-Resistant Tuberculosis (PMDT) for MDR-TB patients.

Treatment success is known to be associated with several factors. These include patient related factors, such as age,¹⁰ gender,¹¹ smoking habit,¹² nutritional status, comorbidities (DM and HIV). *M. tuberculosis* characteristics are also associated with outcome, including number of bacteria and *M. tuberculosis* strain (e.g. Beijing strain).¹³

Data on the prevalence of drug resistance among new or previously treated TB cases is limited to several centers in Indonesia.⁵⁻⁷ This study will be the first to follow new and previously treated TB patients in hospitals in Indonesia. Prevalence data for drug-susceptible and MDR-TB, along with corresponding treatment outcomes, will be beneficial to inform national tuberculosis programs (NTP). Additionally, data collected from this study

will be useful for planning future TB research studies in Indonesia, such as evaluating novel diagnostic test, evaluating markers of response to treatment and identifying new therapies.

2. RESEARCH BENEFITS

2.1 Scientific Benefits

- This study will observe and record TB, drug susceptibility profiles and treatment outcomes of new and previously treated cases.
- The study will observe and record patient demographics, smoking habits, nutritional status, clinical history, bacterial factors (the numbers of bacterial and the infecting strain), and attempt to determine the association between these factors and the success of treatment.
- The study will provide data that is useful for planning future studies in tuberculosis, e.g. basic research, improved diagnostics or clinical trials on newly developed drugs.
- The study will collect samples from participants and may lead to identification of a novel or virulent strain associated with disease and with treatment success. Such information could be extremely important for public health prevention programs.
- 2.2 Community Benefits
 - The study may assist in the development of improved diagnostic and treatment algorithms and processes within hospitals for providing care that can improve patient outcomes.
- 2.3 Policy Benefits
 - Results of this study may provide information that would be valuable to the Ministry of Health and the national tuberculosis program in developing a more effective strategy for treatment and prevention.

3. OBJECTIVES

3.2 Primary Objective

To estimate the proportion of MDR TB amongst new and previously treated TB cases.

- 3.3 Secondary Objective
 - To evaluate accuracy of clinical diagnosis by comparing clinically defined TB

to laboratory confirmed TB.

- To compare AFB and Xpert MTB/RIF as TB diagnostic tests against culture result.
- To estimate the sensitivity and specificity of Xpert MTB/RIF in detecting Rif susceptibility against Drug Susceptibility Test (DST).
- To estimate the proportion of cured, completed, failed, died and lost to follow up as treatment outcomes in drug susceptible TB (DS-TB) cases and drug resistant TB (DR-TB) cases.
- To evaluate the association of treatment success (cured or completed) with the following data:
 - 1. Demographics (age, sex)
 - 2. TB contact history
 - 3. Smoking habit
 - 4. Treatment seeking behavior
 - 5. Co-morbidities (HIV, DM, cancer)
 - 6. Primary and secondary drug resistance
 - 7. Symptoms
 - 8. Cavitary disease
 - 9. Nutritional status
 - 10. Treatment regimens
 - 11. Patient reported compliance
 - 12. Numbers of bacteria by AFB test
 - 13. TB strains (e.g., Beijing)

4. METHODS

4.1 Study Plan

The brief explanation of the study plan will be captured on figure 1.

4.2 Sites and Duration

This study will be conducted at hospitals in the INA-RESPOND network:

- 1. Persahabatan hospital, Jakarta
- 2. [name]. Sulianti Saroso Infectious Diseases hospital, Jakarta
- 3. [name] hospital, Bandung
- 4. [name] hospital, Semarang
- 5. [name] hospital, Surabaya
- 6. Sanglah hospital, Bali

- 7. [name] hospital, Yogyakarta
- 8. [name] hospital, Makassar
- 9. Gatot Subroto Army hospital, Jakarta
- 10. H. Adam Malik Hospital, Medan
- Patients suspected of having pulmonary TB
 - Cough ≥ 2 weeks
 - At least 1 other TB clinical symptoms (fever, unexplained weight loss, loss of appetite, hemoptysis, shortness of breath, chest pain, night sweats, fatigue)
- Suggestive TB on chest x-ray based on pulmonologist or internist consultant of pulmonology opinion
- Age ≥18 years old
- Participants (with or without TB treatment history) are screened whether they meet the following criteria:
 - Willing to be treated or evaluated at study site
 - Willing to have specimens stored for use in future studies
 - Patient denies having TB treatment for maximum 7 days in the last 1 month
 - Pregnancy or any serious condition include, but are not limited to, liver disease, chronic kidney disease, and psychiatric illness, that might interfere with study compliance

[figure not shown]

Figure 1. The Study Plan

The Study will enroll eligible participants for a period of up to 2 years. Participants will be followed up until 6 months' post treatment. For drug susceptible TB, this will be approximately 12 months after enrollment/treatment start, but it may be longer if they have drug resistant TB or require longer treatment regimen for other reasons (e.g. Category 2 treatment, diabetes, etc). For those participants, the study will follow them for maximum 30 months after enrollment/treatment start. Stored specimens will be investigated during the study and/or after study completion.

4.3 Type and Design of Study

This study is a prospective observational cohort study of new and previously treated TB patients. Patients will be treated as per standard of care according to national TB treatment guidelines and each study site policy by each patient' physician. This study will collect data and specimens as outlined in Appendix A. Additional blood, sputum, urine, and saliva specimens will be obtained for TB examinations and stored for related TB future testing.

Study participants will continue to be managed in accordance with the DOTS or PMDT strategy by the patients' physician. Clinical care or treatment for all participants is provided by the healthcare facility based on the National Guidelines or clinician decisions. No intervention either treatment or behavior, applied for this study.

4.4 Population and Sample Size

This is a descriptive study with the goal of estimating rates MDR in two separate cohorts (new and previously treated TB cases). WHO global report in 2013 estimated 1.9% MDR TB cases in new TB cases and 12% MDR TB cases in previously treated TB cases for Indonesia. This study will analyze 250 bacteriologically confirmed new TB participants and 250 bacteriologically confirmed previously treated participants. We estimate that 25% of presumptive new TB participants who satisfy study entry criteria will be bacteriologically confirmed TB. Similarly, we estimate that 70% of previously treated cases will be bacteriologically confirmed TB. Therefore, to obtain 500 bacteriologically confirmed TB cases and 357 presumptive previously treated cases will be enrolled, for a total of 1,357 enrolled. The proportion of confirmed TB cases amongst new and previously treated cases is an estimation and will be re-evaluated during the course of the study. Refer to the interim analysis section below for details.

Table 4.4.1 describes the expected precision (confidence bounds and width) for observed proportion of MDR amongst previously treated cases. With 250 participants and an observed MDR proportion of 12%, the confidence interval will be (0.085, 0.162). The precision of the estimated proportion of MDR does not improve considerably when increasing the sample size to 300. The confidence interval for a sample size of 300 with an MDR proportion of 12% is (0.085, 0.162), while decreasing the sample size to 200 has a more striking impact on the bounds increasing the lower bound to 0.078 and the upper bound to 0.173.

When considering the sample size for new TB cases, we note that the precision of binomial confidence intervals based on exact Clopper Pearson method increases as the proportion gets closer to zero. As a result, we find the true MDR rate is more precisely estimated with a sample size of 250 for new TB cases (compared to previously treated cases, where the MDR rate is expected to be around 12%). With a sample size of 250

new TB cases, the expected 95% confidence interval is (0.007, 0.046). (Table 4.4.1) Exact Clopper Pearson binomial confidence interval method formula:

$$\left(1 + \frac{n - x + 1}{xF\left[1 - \frac{1}{2}\alpha; 2x, 2(n - x + 1)\right]}\right)^{-1} < \theta < \left(1 + \frac{n - x}{[x + 1]F\left[\frac{\alpha}{2}; 2(x + 1), 2(n - x)\right]}\right)^{-1}$$

Table 4.4. 1 Expected confidence bounds based on observed MDR proportions amongst previously treated TB cases.

Sample Size	Observed proportion	Bounds of 95% confidence interval*	Actual width
150	0.12	(0.073, 0.183)	0.110
	0.15	(0.097, 0.217)	0.120
200	0.12	(0.078, 0.173)	0.095
	0.15	(0.104, 0.207)	0.104
250	0.12	(0.082, 0.167)	0.084
	0.15	(0.108, 0.200)	0.092
300	0.12	(0.085, 0.162)	0.077
	0.15	(0.112, 0.196)	0.084
400	0.12	(0.090, 0.156)	0.066
	0.15	(0.116, 0.189)	0.072

* Cls based on Exact Clopper-Pearson method

Table 4.4. 2 Expected confidence bounds based on observed MDR proportions amongst new TB cases.

Sample size	Observed proportion	Bounds of 95% confidence interval*	Actual width
150	0.01	(0.001, 0.042)	0.041
	0.02	(0.004, 0.057)	0.053
	0.03	(0.009, 0.072)	0.062
	0.05	(0.021, 0.098)	0.077
200	0.01	(0.001, 0.036)	0.034
	0.02	(0.005, 0.050)	0.045
	0.03	(0.011, 0.064)	0.053
	0.05	(0.024, 0.090)	0.066
250	0.01	(0.002, 0.032)	0.030
	0.02	(0.007, 0.046)	0.040
	0.03	(0.013, 0.059)	0.047
	0.05	(0.027, 0.085)	0.058
300	0.01	(0.002, 0.029)	0.027
	0.02	(0.007, 0.043)	0.036
	0.03	(0.014, 0.056)	0.042
	0.05	(0.028, 0.081)	0.053

400	0.01	(0.003, 0.025)	0.023
	0.02	(0.009, 0.039)	0.03
	0.03	(0.016, 0.052)	0.036
	0.05	(0.031, 0.076)	0.045

* CIs based on Exact Clopper-Pearson method

The sampling method in this study is purposive sampling. The study will stop recruiting participants when 1,000 new presumptive TB cases and 357 previously treated TB cases had enrolled.

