4.7.2 Analysis

This is an observational study to describe rates of MDR TB amongst new and previously treated TB cases in Indonesia. Risk factors for MDR will be evaluated as a secondary objective. Additional secondary objectives include a description of treatment outcomes (cure, failure, death, completed treatment) and evaluation of associated risk factors for poor outcome, comparison of diagnostic accuracy of AFB and Xpert MTB/RIF (relative to culture) and an estimation of Xpert MTB/RIF Rif susceptibility testing sensitivity and specificity relative to standard DST. Research objectives will be analyzed as described below.

Primary objective

 To estimate the rate of MDR-TB amongst new and retreated TB cases. Proportions of MDR will be estimated, along with exact 95% confidence intervals based on a binomial distribution. Case definitions of MDR, new and previously treated TB are provided in Appendix B.

Secondary objective

- To estimate treatment outcomes (cured, failed, died, treatment completion, and lost to follow up) according to susceptibility pattern. Proportions of participants within each category will be estimated along with confidence intervals. Definitions of treatment outcomes are provided in appendix B.
- 2) To evaluate risk/protective factors for treatment success (cured or completed treatment vs failed or died or loss to follow up). These factors include: demographics (age, sex), TB contact history, smoking habit, treatment seeking behavior, co-morbidities (HIV, DM), primary drug resistance, symptoms, no cavity in the lung, nutritional status, treatment regimens, compliance, numbers of bacteria and TB strains (e.g., Beijing). Logistic regression models will be used to describe associations of treatment success with these factors.
- 3) To evaluate risk/protective factors for treatment interruption (loss to follow up vs other treatment outcome). These factors include: demographics (age, sex), TB contact history, smoking habit, treatment seeking behavior, co-morbidities (HIV, DM, and other comorbidities), primary drug resistance, symptoms, cavity in the lung, nutritional status, treatment regimens, compliance, numbers of bacteria and TB strains (e.g., Beijing). Logistic regression models will be used to evaluate associations of treatment interruption with these risk factors.
- To compare clinically defined TB against laboratory confirmed TB. Accuracy will be estimated along with 97.5% confidence intervals.

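### Section 4.4 states expected precision at the 2013 MDR rates although the Background gives later, higher ones, and its text prints the n = 300 interval for n = 250

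*Combined protocol and SAP*

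**What the plan says.** Section 4.4 (Population and Sample Size) fixes the analysed numbers: "This study will analyze 250 bacteriologically confirmed new TB participants and 250 bacteriologically confirmed previously treated participants". The study is descriptive, so the case for these numbers is the expected interval width. The planning rates are introduced with "WHO global report in 2013 estimated 1.9% MDR TB cases in new TB cases and 12% MDR TB cases in previously treated TB cases".

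For previously treated cases the text reads "With 250 participants and an observed MDR proportion of 12%, the confidence interval will be (0.085, 0.162"), and gives the same pair of bounds again for 300 participants. Table 4.4.1 has (0.082, 0.167), width 0.084, for 250 at 12%, and (0.085, 0.162), width 0.077, for 300 at 12%. Its highest tabulated rate is 15%.

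For 250 new cases, "the expected 95% confidence interval is (0.007, 0.046"), which is the 2% row of Table 4.4.2. That table also covers 1%, 3% and 5%. In comparing the cohorts, the section describes previously treated cases as the group "where the MDR rate is expected to be around 12" per cent.

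Section 1 (Background) reports, from the WHO 2016 report for 2015, "2.9% of new TB cases and 16% of previously treated TB cases are MDR-TB cases". It also cites a 2006 Central Java survey: "1.8% of new TB cases and 17.1% of previously treated TB cases are MDR-TB".

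Section 4.7.2 (Analysis) confirms the method for the primary objective: "Proportions of MDR will be estimated, along with exact 95% confidence intervals based on a binomial distribution".

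**The concern.** The Background and the sizing section of one version rest on different MDR rates. The Background has the later WHO estimates. Section 4.4 uses the 2013 ones, does not mention the later pair, and calls 12% the expected rate. Near these values a binomial interval widens as the proportion rises towards one half, so precision quoted at 12% and 2% is more favourable than precision at 16% and 2.9%.

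The text interval for previously treated cases is a second and separate fault. The same bounds are printed for 250 and for 300 participants, so the sentence arguing that 300 adds little compares an interval with itself.

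Expected precision is the only justification offered for 250 + 250. A sponsor or reader relying on the text of Section 4.4 would expect somewhat tighter primary estimates than the protocol's own later figures imply.

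**Working it through.** **Inputs.** n = 250 per cohort (Section 4.4). Two-sided 95% exact binomial interval (Sections 4.4 and 4.7.2). Rates of 2% (1.9% rounded) and 12% from Section 4.4; 2.9%, 16% and 17.1% from the Background.

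**Formula.** With x = n × p and B(q; a, b) the q-quantile of the beta distribution, the Clopper-Pearson limits are

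- lower = B(0.025; x, n − x + 1)
- upper = B(0.975; x + 1, n − x)

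This is equivalent to the F-quantile form printed in Section 4.4. Fractional x is allowed because the tables do the same: 15% of 250 is 37.5, and that row reproduces.

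**Step 1: the plan's own figures.** All 30 rows of Tables 4.4.1 and 4.4.2 reproduce to rounding. The rows that matter here:

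| n | p | x | interval | width | plan |
|---|---|---|---|---|---|
| 250 | 12% | 30 | (0.0824, 0.1669) | 0.0844 | Table 4.4.1 agrees; text does not |
| 300 | 12% | 36 | (0.0855, 0.1622) | 0.0768 | Table 4.4.1 agrees; same pair printed in the text for n = 250 |
| 250 | 15% | 37.5 | (0.1081, 0.2004) | 0.0923 | Table 4.4.1 agrees |
| 250 | 2% | 5 | (0.0065, 0.0461) | 0.0395 | Table 4.4.2 and text agree |
| 250 | 3% | 7.5 | (0.0126, 0.0595) | 0.0469 | Table 4.4.2 agrees |

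A different method does not explain the text interval. At n = 250 and 12%, Wald gives (0.080, 0.160) and Wilson gives (0.085, 0.166).

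**Step 2: the Background rates at n = 250.**

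| cohort | p | x | interval | width |
|---|---|---|---|---|
| Previously treated | 16% | 40 | (0.1168, 0.2114) | 0.0946 |
| Previously treated | 17.1% | 42.75 | (0.126, 0.224) | 0.0970 |
| New | 2.9% | 7.25 | (0.0120, 0.0582) | 0.0462 |

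For new cases, whole counts bracket the result: 7/250 gives (0.011, 0.057), width 0.045 to 0.046, and 8/250 gives (0.014, 0.062), width 0.048.

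**Step 3: size of the difference.**

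- Previously treated, 16% against the 12% table row: 0.0946 / 0.0844 = 1.12. Half-width grows by (0.0946 − 0.0844) / 2 = 0.0051, about 0.5 percentage points.
- Previously treated, 16% against the interval printed in the text: 0.0946 / 0.0768 = 1.23. Of the gap in width, 0.0946 − 0.0768 = 0.0178, the misprint accounts for 0.0844 − 0.0768 = 0.0076 and the older rate for 0.0946 − 0.0844 = 0.0102.
- New, 2.9% against the 2% row: 0.0462 / 0.0395 = 1.17. Half-width grows by (0.0462 − 0.0395) / 2 = 0.0034, about 0.3 percentage points.

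**Step 4: distance from the rows already tabulated.** The 15% row is short of the 16% width by 0.0946 − 0.0923 = 0.0023. The 3% row (0.0469) is slightly wider than the 2.9% result (0.0462).

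**Step 5: the comparison of 250 with 300.** With the correct interval, going from 250 to 300 at 12% narrows the width from 0.0844 to 0.0768, a reduction of 0.0076 / 0.0844 = 9%. The text as printed shows no reduction.

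**The case against.** The strongest reply is that an interval conditional on an observed proportion is not made wrong by another rate being plausible. The previously treated sentence is worded that way, and so are the headings of both tables. This stands: apart from the misprinted bounds, the mismatch of rates is a matter of consistency and updating, not of arithmetic. It does not remove the point, because the same section calls 12% the expected rate and labels the new-case bounds as expected, so both serve as forecasts.

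A second reply is that the tables already deal with it. This largely stands. The 3% row covers the later new-case rate, and the 15% row comes within 0.002 of the width at 16%. What remains is that the text quotes only the 12% and 2% intervals, and no row reaches 16% or 17.1%.

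A third reply is that nothing fails, since the plan sets no target width. That also stands.

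A reader might go further and infer that the section is wrong to say the new-case rate is estimated with more precision, because the new-case interval is wide relative to so small a proportion. The documents do not support that. Section 4.4 describes precision by bounds and width, and on absolute width the statement is true at the planning rates (0.040 against 0.084) and at the Background rates (0.046 against 0.095). Nor is it a defect that the new-case interval cannot distinguish one cited rate from another: the primary objective is estimation, and no such comparison is planned.

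**Conclusion.** The point holds as two limited corrections to Section 4.4. First, its expected precision rests on the 2013 rates, with no reason given for preferring them to the later rates in the Background. At those later rates, n = 250 gives widths of about 0.095 and 0.046, against 0.084 and 0.040 in the corresponding table rows. Second, the n = 250 text interval at 12% is the n = 300 interval. This is a plain error that Table 4.4.1 itself contradicts.

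It would be tempting to conclude that 250 per cohort is too few. The documents do not support that: there is no target width to miss, and the loss is a fraction of a percentage point of half-width.

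The figures assume, as Section 4.4 does, simple binomial sampling and an MDR classification for all 250 cases in each cohort. They also take the Background's WHO rates as the better current expectation. If the sponsor has grounds for keeping the 2013 rates, a stated reason would settle the first part; the second would still need correcting.

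**What to change.** Keep the sample size. In Section 4.4:

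1. Correct the n = 250 text interval at 12% to (0.082, 0.167), so that the comparison with n = 300 sets 0.084 against 0.077.
2. State the expected n = 250 intervals at the Background rates, about (0.012, 0.058) at 2.9% for new cases and (0.117, 0.211) at 16% for previously treated cases. Alternatively, say why the 2013 rates are kept.
3. Add a 16% row at each sample size to Table 4.4.1, and optionally a 17% row. At n = 250 the 16% entry is (0.117, 0.211), width 0.095.
4. In the same edit, point the new-case interval to Table 4.4.2; the text now cites Table 4.4.1.

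The remark that the new-case rate is the more precisely estimated can stay. The cost is rewording one section and adding rows to one table. The stated precision becomes slightly less favourable, and no further participants are needed.
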